9.7 Safety Analyses

Injection related reactions, AEs, SAEs, and abnormal laboratory values will be summarized by the proportion of patients who experience them.

All patients in the safety population will be used in the safety analyses. Safety analyses will be summarized by dose or analysis group.

The treatment-emergent period is defined in [Section 7.1](#).

9.7.1 Dose Limiting Toxicities

For Dose Escalation purposes, a DLT will be defined as any of the following AEs occurring from the time of the first injection (Day 1) through Study Day 29 of any of the following:

Non-hematologic adverse event

- Grade ≥ 3 non-hematologic AE related to SD-101 (eg, post-injection reaction or influenza-like illness) that does not resolve to Grade ≤ 1 with standard treatment by the time of the next treatment, with the exclusion of fatigue
- Grade 3 non-hematologic AE (not laboratory, specifically nausea, vomiting, and diarrhea) lasting > 3 days despite optimal supportive care, with the following exceptions:
 - Grade 3 fatigue will NOT be classified as a DLT, regardless of duration.
 - A Grade 3 non-hematologic laboratory AE will only be considered a DLT if it is clinically significant, such as:
 - Medical intervention is required to treat the patient
 - The abnormality leads to hospitalization
 - The abnormality persists for > 1 week
- Grade 4 or 5 non-hematologic AE (not laboratory)

Hematologic toxicity

- Grade 4 or 5 hematologic AE
- Any Grade 3 hematologic laboratory AE, with the exception of lymphopenia, which lasts > 7 days
- Febrile neutropenia Grade 3 or Grade 4:
 - Grade 3 is defined as ANC $< 1000/\text{mL}$ with a single temperature of $> 38.3^\circ\text{C}$ (101°F) or a sustained temperature of $\geq 38^\circ\text{C}$ (100.4°F) for more than 1 hour.
 - Grade 4 is defined as ANC $< 1000/\text{mL}$ with a single temperature of $> 38.3^\circ\text{C}$ (101°F) or a sustained temperature of $\geq 38^\circ\text{C}$ (100.4°F) for more than 1 hour, with life-threatening consequences and urgent intervention indicated.

Prolonged delay (> 3 weeks) of SD-101 or pembrolizumab dosing due to treatment-related toxicity qualifies as a DLT.

Incidence of DLTs will be tabulated by dose groups in Phase 1, and bar chart of incidence rates of DLTs by dose groups will be generated, if DLTs were observed.

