4.1.1 Phase 1 Dose Escalation: Melanoma (*COMPLETE*)

The Phase 1 will consist of up to 4 Dose Escalation cohorts to evaluate the safety and tolerability of SD-101 given in combination with pembrolizumab in melanoma populations (anti-PD-1/L1 naïve and anti-PD-1/L1 experienced with progressive disease) to identify an RP2D to be evaluated in Phase 2.

Phase 1 employs a modified 3 + 3 study design, evaluating escalating or intermediate dose levels of SD-101 (given with a fixed dose of pembrolizumab) in patients with metastatic melanoma. Cohorts of 3 to 6 patients will be enrolled at each dose level, and each patient will participate in only 1 cohort. Patients at each dose level will be treated and observed for dose-limiting toxicities (DLTs) through the DLT assessment period (Study Day 1-29). Once an RP2D is declared, an additional 6 patients may be enrolled to assess safety at this dose.

Patients in Escalation Cohorts 1-4 will be administered 2.0 mg, 4.0 mg, 8.0 mg, and 1.0 mg, respectively, of SD-101 in combination with 200 mg pembrolizumab Q3W per the Schedule of Trial Events.

The melanoma Dose Escalation cohorts, patient populations, and treatment assignments are outlined in Table 4-2.

Table 4-2: Phase 1 Melanoma Dose Escalation Cohorts (*COMPLETE*)

Cohort	Anti-PD-1/L1 Experience	SD-101 Dose	n	Dosing Schema ^a
1	Naïve or experienced	2.0 mg per lesion in 1 injectable lesion (Lesion A)	3 - 6	A
2	Naïve or experienced	4.0 mg per lesion in 1 injectable lesion (Lesion A)	3 - 6	A
3	Naïve or experienced	8.0 mg per lesion in 1 injectable lesion (Lesion A)	3 - 6	A
4	Naïve or experienced	1.0 mg per lesion in 1 injectable lesion (Lesion A)	3 - 6	A ^b

Anti-PD-1/L1 = anti-programmed death receptor-1/ligand 1.

^a Dosing Schema:

A: SD-101 and pembrolizumab dosing both start on Day 1 and patients receive 1 course of SD-101 (4 weekly doses and then every 3 weeks on schedule with pembrolizumab for 7 additional doses).

^b 1.0 mg was added at Protocol Amendment 4.

[figure not shown]

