5.1 Inclusion Criteria

A patient must meet all the following criteria to be eligible for enrollment (defined as receiving the first trial treatment [ie, pembrolizumab or SD-101]) in the trial:

Phase 1 and Phase 2

- 1) Willing and able to provide written informed consent for the trial
- 2) Aged 18 years and older
- 3) Eastern Cooperative Oncology Group (ECOG) Performance Status (PS) of 0 or 1
- 4) Patient must have adequate organ function as indicated by the following laboratory values:

Hematological

- Absolute neutrophil count (ANC) $\geq 1,500$ /mcL
- Platelet count $\geq 100,000$ /mcL
- Hemoglobin ≥ 9 g/dL or ≥ 5.6 mmol/L

Renal

- Serum creatinine $\leq 1.5 \times$ upper limit of normal (ULN) OR
- Measured or calculated creatinine clearance (GFR can also be used in place of creatinine or CrCl) ≥ 60 mL/min for subject with creatinine levels $> 1.5 \times$ institutional ULN

Hepatic

- Serum total bilirubin:
 - $\leq 1.5 \times$ ULN **OR**
 - $< 3 \times$ ULN for persons with Gilbert's syndrome **OR**
 - Direct bilirubin \leq ULN for patients with total bilirubin levels $> 1.5 \times$ ULN
- Aspartate transaminase (AST) and alanine transaminase (ALT) (also known as serum glutamic oxaloacetic transaminase and serum glutamic pyruvic transaminase)
 - $\leq 2.5 \times$ ULN **OR**
 - $\leq 5 \times$ ULN for patients with liver metastases

Coagulation

- International normalized ratio or prothrombin time (PT) $\leq 1.5 \times$ ULN unless patient is receiving anticoagulant therapy, and as long as PT or partial thromboplastin time (PTT) is within therapeutic range of intended use of anticoagulants
 - Activated partial thromboplastin time (aPTT) $\leq 1.5 \times$ ULN unless patient is receiving anticoagulant therapy, and as long as PT or PTT is within therapeutic range of intended use of anticoagulants
- 5) Have provided 2 tissue biopsy samples taken of the target lesion (Lesion A) as a single biopsy split into 2 samples or 2 separate biopsies that meet the minimal sample size requirement per the study laboratory manual. One sample is for determining PD-L1 expression level by immunohistochemistry and can be an archival sample of the anticipated target lesion that has been collected within 3 months of screening. The other sample is for RNA expression profiling and must be a fresh biopsy.
- 6) Life expectancy of at least 6 months

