12.0 STATISTICAL METHODS

NOTE: As of Amendment 9, Phase 1 of the trial is complete. All analyses related to data collected in Phase 1 will be performed as detailed in this section. As of Amendment 9, the trial will stop collecting efficacy and exploratory data, and the collection of safety data has been simplified. Thus, after trial completion, only selected analyses related to data collected in Phase 2 of the trial will be performed, and exploratory objectives will not be pursued.

This section outlines the statistical analysis strategy and procedures for the trial. If, after the trial has begun, changes are made to primary or exploratory objectives and/or hypotheses, or to the statistical methods related to those objectives and/or hypotheses, then those changes, along with an explanation as to when and why they occurred, will be listed in the Clinical Study Report (CSR) for the trial. Post hoc exploratory analyses will be clearly identified in the CSR. No imputations will be made for missing data. Additional details of the statistical analyses to be performed will be provided in the trial Statistical Analysis Plan.

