12.3 Analysis Endpoints

12.3.1 Safety Endpoints

The primary safety endpoint in Phase 1 of the trial is incidence of DLTs. Other safety measures evaluated in all parts of the trial are injection-site reactions, all other AEs, laboratory safety assessments, and vital signs.

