12.7 Safety Analyses

All safety data will be analyzed descriptively and will be based on the all-treated population. The most important safety parameters will be presented for all sites combined. Summary statistics will be used to describe the incidence of all injection-site reactions, AEs, SAEs, deaths, and laboratory values. DLTs occurring in Phase 1 will be summarized by dose level received and presented in both tables and listings.

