9.7.1 Dose Limiting Toxicities

For Dose Escalation purposes, a DLT will be defined as any of the following AEs occurring from the time of the first injection (Day 1) through Study Day 29 of any of the following:

Non-hematologic adverse event

- Grade ≥ 3 non-hematologic AE related to SD-101 (eg, post-injection reaction or influenza-like illness) that does not resolve to Grade ≤ 1 with standard treatment by the time of the next treatment, with the exclusion of fatigue
- Grade 3 non-hematologic AE (not laboratory, specifically nausea, vomiting, and diarrhea) lasting > 3 days despite optimal supportive care, with the following exceptions:
 - Grade 3 fatigue will NOT be classified as a DLT, regardless of duration.
 - A Grade 3 non-hematologic laboratory AE will only be considered a DLT if it is clinically significant, such as:
 - Medical intervention is required to treat the patient
 - The abnormality leads to hospitalization
 - The abnormality persists for > 1 week
- Grade 4 or 5 non-hematologic AE (not laboratory)

Hematologic toxicity

- Grade 4 or 5 hematologic AE
- Any Grade 3 hematologic laboratory AE, with the exception of lymphopenia, which lasts > 7 days
- Febrile neutropenia Grade 3 or Grade 4:
 - Grade 3 is defined as ANC $< 1000/\text{mL}$ with a single temperature of $> 38.3^\circ\text{C}$ (101°F) or a sustained temperature of $\geq 38^\circ\text{C}$ (100.4°F) for more than 1 hour.
 - Grade 4 is defined as ANC $< 1000/\text{mL}$ with a single temperature of $> 38.3^\circ\text{C}$ (101°F) or a sustained temperature of $\geq 38^\circ\text{C}$ (100.4°F) for more than 1 hour, with life-threatening consequences and urgent intervention indicated.

Prolonged delay (> 3 weeks) of SD-101 or pembrolizumab dosing due to treatment-related toxicity qualifies as a DLT.

Incidence of DLTs will be tabulated by dose groups in Phase 1, and bar chart of incidence rates of DLTs by dose groups will be generated, if DLTs were observed.

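### The febrile-neutropenia DLT cut-off in SAP 9.7.1 is printed per mL, 1000-fold out of unit with the plan's other ANC thresholds; a minor correction with no result shown to change

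*SAP*

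**What the plan says.** Under hematologic toxicity, SAP 9.7.1 counts febrile neutropenia of Grade 3 or 4 as a DLT and gives each grade a neutrophil cut-off together with a fever criterion. For Grade 3: "Grade 3 is defined as ANC $< 1000/\text{mL}$ with a single temperature". For Grade 4: "Grade 4 is defined as ANC $< 1000/\text{mL}$ with a single temperature", with life-threatening consequences added. Protocol 9.1 carries the same two lines, and nothing in either document explains or corrects the unit.

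Elsewhere the unit is the microlitre. Protocol 5.1 requires "Absolute neutrophil count (ANC) $\geq 1,500$ /mcL" for entry. Protocol 7.1 requires at least 1500 cells/mcL to give SD-101, and Protocol 7.6 holds SD-101 below 1500 cells/mcL.

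The definition belongs to an endpoint that is still to be reported. Protocol 12.3.1 states: "The primary safety endpoint in Phase 1 of the trial is incidence of DLTs". Of Phase 1, Protocol 12.0 says: "All analyses related to data collected in Phase 1 will be performed as detailed in this section". Protocol 12.7 adds: "DLTs occurring in Phase 1 will be summarized by dose level received". Below the definition, SAP 9.7.1 plans the table: "Incidence of DLTs will be tabulated by dose groups in Phase 1".

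**The concern.** A threshold of 1 neutrophil per microlitre is in practice no neutrophils at all. It cannot be what is meant in a plan that already withholds the drug below 1500 per microlitre. The line is a decision threshold inside the definition of the Phase 1 primary safety endpoint, and the SAP prints it in the section that plans the DLT table. If the text were applied as printed, some febrile patients with clearly low counts would not qualify through this line. At stake is whether the written definition matches the one that was actually used, and whether the study report will repeat a cut-off that is wrong on its face.

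**Working it through.** The cut-off is a stated definition with no calculation behind it, so there is no figure of the plan's own to reproduce. The check is a unit conversion, followed by a comparison with the other DLT criteria.

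**Inputs**
- DLT cut-off as printed, both grades: 1000 per mL (SAP 9.7.1; Protocol 9.1)
- Eligibility: at least 1500 per mcL (Protocol 5.1)
- Dosing condition: at least 1500 per mcL (Protocol 7.1)
- SD-101 hold: below 1500 per mcL (Protocol 7.6)
- 1 mL = 1000 mcL

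**Conversion**
- As printed: 1000 / 1000 = 1 cell/mcL, or 0.001 x 10^9/L.
- Hold threshold: 1500 x 1000 = 1,500,000 cells/mL, or 1.5 x 10^9/L.
- The printed cut-off as a share of the hold threshold: 1 / 1500 = 0.067%.
- With the unit used elsewhere: 1000 cells/mcL = 1,000,000 cells/mL, or 1.0 x 10^9/L. This is 1000 times the printed value and lies just below the 1500 per mcL dosing threshold.

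**Who meets the neutrophil part of the definition, given the fever criterion**

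| ANC, cells/mcL | As printed (< 1) | Per mcL (< 1000) |
|---|---|---|
| 0.5 | yes | yes |
| 1 | no | yes |
| 50 | no | yes |
| 400 | no | yes |
| 999 | no | yes |
| 1000 | no | no |

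The two readings differ for counts from 1 up to, but not including, 1000 cells/mcL.

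**Which of those events another DLT criterion still catches** (same list in SAP 9.7.1 and Protocol 9.1)

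| Event | Caught elsewhere? |
|---|---|
| Grade 4 febrile neutropenia | Yes: any hematologic event of Grade 4 or 5 is a DLT |
| Grade 3, with a concurrent Grade 4 hematologic event | Yes: same criterion |
| Grade 3, with a Grade 3 hematologic laboratory abnormality lasting more than 7 days | Yes: duration criterion (lymphopenia excepted) |
| Grade 3, delaying either drug by more than 3 weeks | Yes: delay criterion |
| Grade 3, resolved within 7 days, none of the above | No |

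Only the last row depends on the unit. The Grade 4 line has the same slip but cannot remove an event.

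**The case against.** The strongest reply is that nobody would apply the printed number. The parent item names febrile neutropenia of Grade 3 or 4 as the DLT, and Protocol 9.1 requires all adverse events, DLTs included, to be graded by CTCAE v4.03. Under Protocol 9.1.2, cohort data were reviewed for DLTs before each escalation. The definition is introduced as serving dose escalation, which is over. Neither SAP 9.7.1 nor Protocol 12.7 says that the statistician will re-derive DLTs from counts and temperatures. The table may simply report the DLTs as judged at the time. Most of this stands, and it limits the point to a correction of text. What it leaves is a written definition that readers must silently override.

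The second reply is that the unit may be a conversion fault: a microlitre sign lost from the PDF would look exactly like this. That cannot be excluded. The other thresholds are spelled with plain letters, so their correct reading proves little. The SAP repeats the Protocol's wording, so the two do not confirm each other independently. Against a misread, mL appears in both grade lines of both documents, and the micro sign survives in the mouse doses in Protocol 2.5. A misread looks unlikely, but the source should be checked before anything is changed.

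**Conclusion.** As printed, the cut-off is wrong by a factor of 1000 and should be corrected. The consequence is narrow: under a literal reading, only short Grade 3 febrile neutropenia with no other qualifying feature would go uncounted. Severity is minor. Confidence is medium, and rests on two assumptions: that the source PDF shows the same unit, and that the intended value is 1000 per mcL. The second is inferred from the plan's other thresholds, since neither document reproduces the CTCAE entry.

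A reader might infer that a DLT was missed, that a dose was wrongly declared tolerated, or that a reported rate is off. The documents support none of these. Protocol 2.6 reports no DLTs for SD-101 with pembrolizumab, no febrile-neutropenia event is described, and Phase 1 is complete with its dose decisions made. The planned groups are small ("Cohorts of 3 to 6 patients will be enrolled at each dose level"), so any single event would weigh heavily. But actual group sizes are not given and no event is shown, so no shift in a DLT rate can be attached to this point.

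**What to change.** 1. Confirm the unit against the source PDFs of both documents, and the intended value with the sponsor.
2. If the unit is as printed, change both febrile-neutropenia lines in SAP 9.7.1 to ANC < 1000/mcL and file a clarification note for Protocol 9.1. No amendment is needed for a completed phase.
3. When the DLT table is produced, look through the treatment-emergent adverse-event listing already planned in SAP 9.7.3 for febrile neutropenia in Days 1 to 29 of Phase 1, so that the count is confirmed under the corrected cut-off.
4. State the corrected cut-off in the study report.

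The cost is two lines of SAP text, one note, one look-up in an existing output and one sentence in the report. No new data are needed.

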9.7.2 Injection Related Reactions

Incidence of injection-site reactions from the diary card will be tabulated by maximum severity and injection and by analysis group.

Injection related general body symptoms, defined as those symptoms, as determined by the Medical Monitor, with onset with 7 days of and related to the study injection, will be tabulated by maximum severity and injection and by analysis group.

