[Figure 4-1](#) presents the study design for Phase 1 and Phase 2 at Amendment 9.

Figure 4-1: DV3-MEL-01 Study Design Schema at Amendment 9 – Phase 1 and Phase 2

[figure not shown]

Figure 4-1 Footnotes

Anti-PD-1/L1 = anti-programmed death receptor-1/ligand 1; HNSCC = head and neck squamous cell carcinoma; RP2D = recommended Phase 2 dose.

- ^a 1.0 mg of SD-101 was added at Amendment 4
- ^b At Protocol Amendment 5, enrollment in Dose Escalation Cohorts 1-4 was CLOSED. Based on available data (including efficacy, safety, and pharmacodynamics biomarkers), the sponsor selected 8.0 mg in a single injectable lesion if 1 lesion is selected or 2.0 mg per lesion if 2 to 4 lesions are selected for injection as the RP2D to be evaluated in the Dose Expansion phase.
- ^c At Protocol Amendment 6 and based on available data (including efficacy, safety, and pharmacodynamics biomarkers), the sponsor selected a second Phase 2 dose of 2.0 mg per lesion in 1 to 4 injectable lesions to be evaluated in the Dose Expansion phase. Expansion Cohorts 1, 2, 3, and 4 in which patients were treated with 8.0 mg in a single injectable lesion were CLOSED to further enrollment. Cohort 5 (melanoma anti-PD-1/L1 –naïve), Cohort 6 (HNSCC anti-PD-1/L1 –naïve), and Cohort 7 (HNSCC anti-PD-1/L1 –refractory or resistant) were ADDED with patients receiving 2.0 mg per lesion in 1 to 4 injectable lesion(s).
- ^d At Protocol Amendment 7 and based on available data (including efficacy, safety, and pharmacodynamics biomarkers), Cohort 8 (melanoma anti-PD-1/L1–refractory or resistant) was ADDED with patients receiving 2.0 mg per injection in 1 to 4 injectable lesions/regions.
- ^e For Protocol Amendment 9 and based on available data from the ongoing trial (including efficacy, safety, and pharmacodynamics biomarkers), Cohorts 5 and 6 were CLOSED. Additionally, Cohort 8 (melanoma anti-PD-1/L1–refractory or resistant) was expanded to approximately 50 patients.

Note: For Protocol Amendment 9, enrollment is closed for all cohorts. Enrolled patients should continue to receive their assigned trial treatments as per the protocol.

The status of cohorts for this DV3-MEL-01 protocol at Amendment 9 is in Table 4-1.

Table 4-1: Status of Cohorts for DV3-MEL-01 Protocol at Amendment 9

Cohort	Anti-PD-1 /L1 Treatment Status	Orig	A 1	A 2	A 3	A 4	A 5	A 6	A 7	A 8	A9
Ph 1 Mel – 1	Naïve or experienced	X	X	X	X	X	Closed	Closed	Closed	Closed	Complete

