10.3.8 Injection-site Reaction Assessments

Assessments of injection-site reactions will be collected for a minimum of 90 minutes following each of the first 4 initial weekly SD-101 injections in Phase 1 as outlined in the Schedule of Trial Events ([Appendix 1](#) through [Appendix 4](#)) at the clinical site and as reported by the patient on the Diary Card for 7 days in Phase 1.

With Protocol Amendment 6, Diary Cards are discontinued in Phase 2; however, injection site reactions listed on the Toxicity Grading scale for Healthy Adult and Adolescent Volunteers Enrolled in Preventive Vaccine Clinical trials ([Appendix 5](#)) that persist for more than 7 days will be recorded as AEs (Section 11.1).

Prior to the first 4 initial weekly injections of SD-101 in Phase 1 ([Appendix 1](#)), patients will receive a new Diary Card with instructions to measure and record local injection-site reactions and solicited AEs that occur post SD-101 injection. The completed Diary Cards will be reviewed with the patients at their next study visit.

For the first 4 weekly injections of SD-101 in the first course in Phase 1, Dynavax will capture all injection-site reactions that occur, even if the diameter of the largest dimension does not meet a Grade 1 on the severity scale ([Appendix 5](#)). As such, any reaction smaller than this size cannot be graded, but will still be recorded in the clinical database and the severity will be marked as *not applicable (N/A)*.

All data documented by the patient on Diary Cards will be collected, reviewed by the trial nurse/coordinator with the patient, and recorded on the appropriate CRF.

Injection-site reactions need to be recorded also on the AE eCRF for the following:

- 1) The duration of the injection-site reaction exceeds 7 days
- 2) The verbatim term for the injection-site reaction is different than the terms listed for the diary and provided for recording on the injection-site reaction eCRF
- 3) The injection-site reaction qualifies as an SAE.

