APPENDIX 1-4 FOOTNOTES (CONT'D)

Review AEs ^k	In Phase 1, assessments of injection-site reactions will be collected for a minimum of 90 minutes through the first 4 weekly injections and for 30 minutes following the remaining injections of SD-101 at the clinical site. Injection-site reactions will be graded based on the Toxicity Grading Scale for Healthy Adult and Adolescent Volunteers Enrolled in Preventive Vaccine Clinical Trials (Appendix 5). In Phase 2, injection-site reactions that persist for more than 7 days will be recorded as AEs. All other AEs and laboratory safety measurements will be graded per NCI CTCAE Version 4.03. All AEs, whether gradable by CTCAE or not, will also be evaluated for seriousness. AEs will be collected through 28 days after the last dose of trial treatment.
Concomitant medications ^l	All concomitant medications taken by the patient from Screening through the EOS visit will be reported.
HIV and hepatitis testing ^m	Serum hepatitis B, hepatitis C, and HIV testing as determined by laboratory tests for HBsAg, anti-HBc, and anti-HBs; anti-HCV; and anti-HIV -1/2, respectively. For HNSCC patients only, HPV status (positive + or negative) at Screening will be determined from either archival test results or new testing.
Serum chemistry and CRP ⁿ	Per local standard of care at the discretion of the investigator.
Hematology ^o	Per local standard of care at the discretion of the investigator.
Coagulation ^p	Per local standard of care at the discretion of the investigator.
Thyroid function tests ^q	Per local standard of care at the discretion of the investigator.
Pregnancy testing ^r	For WOCBP, serum or urine pregnancy test must be negative within 72 hours prior to the first trial treatment. If the urine test is positive or cannot be confirmed as negative then a serum test is required which must be negative for the patient to enroll. Dipstick can be used. Additional pregnancy testing should be scheduled per local regulations where applicable. All female patients are considered to be WOCBP except if they have been postmenopausal for at least 2 years or surgically sterile for at least 1 year.
Blood for IFN-alpha inducible gene expression (pharmacodynamic) ^s	Phase 1 Dose Escalation Cohorts 1-4 only: IFN-inducible gene expression measured at pre-dose on Day 1 (baseline), at Day 8 prior to injection, and at Day 9 which is 24 hours after injection.

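### SAP 9.7.2 takes injection-site reactions only from diary cards, but Cohorts 5-8 (48% of planned Phase 2, all 2 mg) opened when or after Phase 2 diaries stopped, and the safety denominator counts them as reaction-free

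*SAP*

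**What the plan says.** - **Source.** SAP 9.7.2: "Incidence of injection-site reactions from the diary card will be tabulated by maximum severity and injection and by analysis group".
- **Denominator.** SAP 9.7: "Injection related reactions, AEs, SAEs, and abnormal laboratory values will be summarized by the proportion of patients who experience them". The same section uses every safety-population patient, and SAP 6.2 defines these as enrolled patients with at least one SD-101 dose. SAP 7.2 bases safety percentages on the analysis population. A separate line in SAP 7.2 uses patients with nonmissing data for by-visit observed-data analyses.
- **Diaries.** Protocol 10.3.8: "With Protocol Amendment 6, Diary Cards are discontinued in Phase 2".
- **Cohorts.** Protocol 4.1 (Figure 4-1 footnotes, Table 4-1) adds Cohorts 5, 6 and 7 at Amendment 6 at 2.0 mg per lesion. Cohort 8 came at Amendment 7 and "was ADDED with patients receiving 2.0 mg per injection in 1 to 4 injectable lesions/regions".
- **What Phase 2 still records.** Footnote k to Protocol Appendices 1-4: "In Phase 2, injection-site reactions that persist for more than 7 days will be recorded as AEs". Protocol 10.3.8 also sends serious reactions to the AE eCRF, and those meeting this condition: "The verbatim term for the injection-site reaction is different than the terms listed for the diary".
- **Columns.** SAP 2.0 pools Phase 1 and Phase 2 by tumor type and prior anti-PD-1/L1 exposure. SAP 9.11 sets 2 mg and 8 mg side by side within each group.

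**The concern.** The SAP is dated November 2019 and written against Amendment 8, after diaries had stopped, yet it neither mentions the change nor limits the table to patients who had a diary. The gap follows dose. Cohorts 5-8 are all 2 mg, while the 8 mg columns draw on Phase 1 and Cohorts 1-4, which opened before diaries stopped. Under the safety-population denominator, a patient who was never asked is tabulated like a patient who had no reaction.

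After Amendment 9, Protocol 4.3.2.2 retains a single Phase 2 endpoint line, and injection-site reaction incidence is part of it. Protocol 2.6 says the recommended dose was updated to 2.0 mg. The display would therefore make local tolerability look better at the dose carried forward, for a reason that has nothing to do with the drug.

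**Working it through.** **Planned totals (Protocol 4.1, SAP 2.0).** Melanoma: 60 + 25 + 25 + 50 = 160. HNSCC: 4 × 25 = 100. Phase 2: 260. Adding 24 in Phase 1 gives 284, the plan's own figure. (SAP 5.0 and Protocol 12.2 also give about 210 for Phase 2, which does not match the cohort list; 260 is used here.)

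**Share without diaries.** Cohorts 5-8: 25 + 25 + 25 + 50 = 125. 125/260 = 48.1%. By tumor: 75/160 = 46.9% melanoma and 50/100 = 50% HNSCC.

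**Safety-population denominator.** The highest rate a column can show, if every diary patient reacts, is diary patients / (diary patients + patients without diaries). Unknowns: n1, the Phase 1 2 mg patients (3 to 6, Protocol Table 4-2); e, how many of these are anti-PD-1/L1 experienced; c1, the Cohort 1 patients at 2 mg per lesion (0 to 60). Neither e nor c1 is stated.

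- MEL/EXP 2 mg = e / (e + 50)
- MEL/NAIVE 2 mg = (n1 − e + c1) / (n1 − e + c1 + 25)
- HNSCC 2 mg, each group = 0 / 25

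At protocol cohort doses with n1 = 6, reading across each row because both columns share the same six patients:

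| e | MEL/EXP | MEL/NAIVE, c1 = 0 | c1 = 30 | c1 = 60 |
|---|---|---|---|---|
| 6 | 6/56 = 10.7% | 0/25 = 0% | 30/55 = 54.5% | 60/85 = 70.6% |
| 3 | 3/53 = 5.7% | 3/28 = 10.7% | 33/58 = 56.9% | 63/88 = 71.6% |
| 0 | 0/50 = 0% | 6/31 = 19.4% | 36/61 = 59.0% | 66/91 = 72.5% |

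**SAP 2.0 grouping.** SAP 2.0 lists 2 mg/lesion patients in Cohorts 2, 3 and 4; Protocol Tables 4-3 and 4-4 list those cohorts at 8.0 mg only. If all 25 in each were at 2 mg and had diaries, the ceilings become (6 + 25)/(6 + 25 + 50) = 31/81 = 38.3% for MEL/EXP and 25/(25 + 25) = 50% for each HNSCC group.

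**Nonmissing denominator.** Patients without diaries drop out, so nothing is diluted. At protocol doses both HNSCC 2 mg cells have n = 0, and MEL/EXP 2 mg has n of at most 6. For scale, 3/6 has an exact (Clopper-Pearson) 95% interval of 11.8% to 88.2%.

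**The case against.** **The denominator is not certain.** The table is by injection, so the by-visit nonmissing rule might be applied, and the TFL specifications that SAP 9.0 refers to are not among these documents. This stands in part. A reader might infer that the display is biased whichever rule is used. It is not: under the nonmissing rule the 2 mg cells are uninformative rather than biased. But SAP 9.7 names injection related reactions expressly and assigns them the safety population, so dilution is what the SAP text produces as written. The no-imputation statements in SAP 7.2 and 7.3 do not help, because leaving a value missing does not remove the patient from the denominator.

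**The HNSCC columns may not be empty.** A reader might infer that they must be. That holds only if the protocol dose tables prevail over SAP 2.0.

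**Six Phase 1 patients is not a strict cap.** Protocol 4.1.1 allows six more at a declared RP2D; twelve would give 12/62 = 19.4% for MEL/EXP at protocol doses. Table 4-2 and closure at Amendment 5 make this unlikely.

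**Other data may exist.** A reader might infer that short-lived reactions in Cohorts 5-8 are lost. The documents do not establish this. Appendix 4 still schedules an injection-site assessment on Days 1, 8, 15 and 22, Protocol 10.0 requires scheduled results on the CRF, and Protocol 10.3.8 refers to an injection-site reaction eCRF. Against that, footnote k mentions only reactions lasting over 7 days for Phase 2. The point is open, and SAP 9.7.2 does not use these assessments.

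**The TEAE tables and descriptive intent.** Prolonged, serious and off-list reactions do reach SAP 9.7.3; shorter listed ones do not. All analyses are descriptive, but a descriptive percentage still needs a denominator that matches who was observed.

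**Conclusion.** The point holds. The diary is the sole stated source, Phase 2 diaries stopped at Amendment 6, and 125 of 260 planned Phase 2 patients (48.1%), all at 2 mg, entered cohorts opened at that amendment or the next. Under the SAP's stated safety denominator they count as non-reactors, which lowers 2 mg relative to 8 mg.

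The size depends on facts the documents leave open. With up to six Phase 1 2 mg patients, the MEL/EXP 2 mg ceiling is 10.7% at protocol doses and up to 38.3% under SAP 2.0. Each HNSCC 2 mg ceiling is 0%, or up to 50%. MEL/NAIVE 2 mg lies anywhere from 0% to 72.5%. All use planned sizes and assume every diary patient reacts, so observed rates would be no higher. The 8 mg columns may also be incomplete if patients in Cohorts 1-4 were still in their diary period when Amendment 6 took effect. Phase 1 dose-group results are unaffected. Confidence is high on the timing and source, and lower on the size of the distortion. This should be fixed before the tables are run.

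**What to change.** In SAP 9.7.2:

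1. Restrict the diary table to patients issued a diary, use patients with diary data for that injection as the denominator, and show that n in every cell.
2. Mark cells without diaries 'not collected', and footnote that Phase 2 diaries ended at Amendment 6, so Cohorts 5-8 had none and some in Cohorts 1-4 may be cut short.
3. Establish whether the clinic injection-site assessments scheduled in Appendices 2-4 are in the database. If they are, tabulate them across doses as the common source.
4. If they are not, show AE-eCRF reactions (over 7 days, serious, or off-list) by analysis group. Footnote the grading scale, because Protocol 9.0 and 11.1 use the Appendix 5 scale for listed reactions while SAP 9.7.3 uses CTCAE. Footnote also that diary patients were prompted to record reactions and Cohorts 5-8 were not.
5. Reconcile SAP 2.0 with Protocol Tables 4-3 and 4-4 on the Cohort 2-4 doses, since this sets column membership.

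The cost is SAP wording, a table shell, footnotes and one database check. No new data are needed. If only AE-eCRF data exist for Cohorts 5-8, comparison of short-lived reactions across doses will remain limited, and the report should say so.
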